**Overview:** The proposed study will evaluate the feasibility and efficacy of a real-time smoking intervention as an adjunct to enhance standard tobacco treatment. 50 adult smokers will be randomly assigned to a control group (standard tobacco treatment, ST, n=25) vs. an experimental group (standard treatment plus a real-time smoking intervention, ST+, n=25). Randomization to group (1:1) will be stratified by average number of cigarettes smoked per day at baseline (< or ≥ 10 cigarettes per day) to balance groups on smoking intensity. Enrolled participants will complete research visits at 4 weeks and 8 weeks (see Figure 1). Participants will receive financial compensation for their time spent completing research activities: \$20 for each appointment (week 0,4,8) for a total of \$60. Participants will earn a \$20 bonus for attending the last visit (week 8) and returning the smartband and charger. These visits will take place remotely in which the participant will speak with our research staff by phone or video call, at the tobacco clinic, at our research office, or at a location that is convenient, such as a public place.

**Recruitment:** We will recruit from the Yale Tobacco Treatment Service (TTS) and the Winchester chest clinic. These programs are a specialized outpatient services at Yale-New Haven Hospital that provides individual tobacco treatment to a large patient

population of current smokers. New patients referred to the TTS and Winchester chest clinic will be informed about the study and will be invited to set up a screening appointment if interested. To facilitate participant enrollment and retention, study procedures may take place in person or remotely (e.g., phone, secure video conference) when possible.

Screening Assessments: To screen for eligibility, participants will complete the following assessments including: 1) Smoking history to assess smoking quantity and frequency such as number of cigarettes per day and number of years smoked, 2) self-reported other tobacco and drug use for the past 30 days. Participants may also complete biochemical verification of smoking status, such as breath carbon monoxide (CO) measured in parts per million or cotinine measured in a small sample of urine or saliva.

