Experimental Methods: Eligible participants will be randomized to one of two treatment conditions (ST vs. ST+). All participants will receive standard outpatient tobacco treatment (ST) at the Yale Tobacco Treatment Service (TTS) or Winchester chest clinic following clinical practice guidelines. All patients receive up to 8 sessions of one-on-one counseling which focuses on setting a quit date within the first 2 weeks of treatment and discusses coping strategies and relapse prevention. Patients are encouraged to try smoking cessation pharmacotherapy and can obtain these medications over the counter or by prescription from the TTS or Winchester chest clinic. The experimental group (ST+) will receive standard care plus an adjunct treatment which involves wearing a smartband for the 8-week study and receiving real-time notifications as soon as smoking is detected with the embedded geospatial movement sensors in the smartband. There are multiple commercially available smartbands/smartwatches that are compatible with the real- time smoking monitoring system; for example, the Asus Zenwatch 2 pairs with the user's smartphone via Bluetooth connection. When smoking is detected, an alert is sent to the user through the band (vibration) and their smartphone app (alert) with a message indicating that smoking was just detected. The user can indicate yes/no if this smoking detection was accurate. Real-time smoking data is recorded for the user to review in their smartphone app and is available for the research team to view on a password-protected secure online dashboard. Data include only the timing and number of smoking events, labeled by subject ID. This real-time notification may disrupt the automaticity of smoking behavior and help bring awareness to smoking and related cues in the moment, which may enhance the individual's ability to anticipate and respond adaptively to cues in the future. The control group will also receive the smartband to wear for the 8 week study to control for demands associated with remembering to wear the band and charge it.

Measures: Baseline measures will be used to characterize the sample. Repeated measures will be used to assess changes in smoking and related constructs during treatment.

Demographic Questionnaires (week 0): Age, gender, marital status, employment status, occupation.

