Smoking History (week 0): Smoking characteristics will be assessed, including the number of years of cigarette use, length of prior quit attempts, and prior treatments used.

Quitting Motivation and Confidence (week 0): Readiness to quit smoking and confidence quitting smoking will be measured on an 11-point scale (0=not at all, 10=extremely) using the contemplation ladder.

Discounting task (week 0): A brief computerized discounting task will be administered (5 questions each) to assess choice preference for cigarettes and money. Participants choose between a hypothetical smaller sooner reward or larger later reward, which is a validated measure of decision-making that has been shown to relate to treatment outcomes.

Timeline Follow-Back Interview (TLFB) (week 0,4,8): A standardized, validated, and reliable interview will be used to obtain quantity and frequency estimates of tobacco use, alcohol, and other drugs for the 30-days prior to baseline and at each research visit.

Biochemical Verification of Smoking Status (week 0,4,8): Assessed when needed to confirm reported abstinence via either expired breath carbon monoxide (CO) levels, which have a half-life of 2 hours or cotinine measured in a small sample of urine or saliva.

Nicotine Dependence (week 0,8): Measured by the Fagerström Test for Nicotine Dependence and the 4-item NIH PROMIS® measure for daily smokers.

Craving (week 0,4,8): Measured by the Questionnaire of Smoking Urges-Brief (QSU-Brief).

Strength of Smoking Habit (week 0,4,8): Measured with a 6-item Self-Report Habit index adapted and validated for smoking behavior, e.g. “Smoking is something I do automatically” rated on a 5-point scale (1=strongly disagree, 5=strongly agree).

Perceived Control Over Smoking (week 0,4,8): Measured with 3 valid, reliable items rated on a 7-point scale that have demonstrated associations with smoking outcome, e.g., “How much control do you feel you have over not smoking?” (1=no control, 7=complete control).

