Approach-Avoidance Task (AAT) (week 0, 4, 8): An objective behavioral task that measures the tendency to automatically approach smoking stimuli (e.g., cigarettes). Our research team has used an adapted version of the approach-avoidance task (AAT) to measure smoking approach and avoidance action tendencies. The task starts with 20 practice trials in which participants learn to push or pull the joystick in response to picture format (landscape or portrait). The practice phase is followed by 160 test trials in which pictures of cigarette stimuli (e.g., cigarettes, cigarette packages) and non-cigarette stimuli (e.g., pencil) come equally in

push- or pull-format (this takes 5 to 10 minutes). Picture format (landscape or portrait) to response assignment (push or pull) is counterbalanced, with half the participants pulling landscape pictures and half portrait pictures. The smoking approach bias represents the relative difference between pushing and pulling the joystick in response to the smoking stimuli, measured as mean reaction time. Evidence supports reliable approach tendencies related to substance use and indicates that meaningful changes in automatic approach tendencies related to substance use outcomes can be detected after one week.

End of Treatment Ratings (week 8): We will evaluate participant satisfaction and perceived usefulness of the treatment across both conditions with post-treatment interviews and ratings.

Analytical Plan:

Data Management and Statistical Analyses: The proposed study will follow HIPAA guidelines for data collection, management, and monitoring. Data analyses will use the intention-to-treat (ITT) principle, where missing data will be treated as smoking. Data analyses will be conducted under the supervision of [name] who is a biostatistician. Data on quantitative outcomes will be examined for conformity to the normal distribution and transformation or non-parametric methods will be used if necessary.

Aim 1: Evaluate the feasibility, acceptability, and helpfulness of the real-time smoking intervention. We will use descriptive statistics to summarize participant ratings of satisfaction and perceived usefulness of the intervention at the end of treatment, including characterizing adherence and feasibility of using the smartband device based on self-report and objective adherence (i.e., number of days wearing the smartband).

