Aim 2: Assess the preliminary efficacy of the real-time intervention as an adjunct to standard tobacco treatment. We will compare biochemically confirmed 7-day point prevalence abstinence at the end of treatment (i.e., reported abstinence from cigarettes during the last week of the study that is confirmed with CO≤ 4ppm or cotinine measured in a small sample of urine or saliva) to estimate effect sizes for ST+ vs. ST. We will also compare continuous outcome measures between ST+ and ST that are proximal indices of good clinical response: number of days abstinent and changes in cigarettes per smoking day from baseline to week 8. We will use independent sample t-tests to compare total days abstinent between ST+ and ST and a 2x2 mixed ANOVA (time x condition) to compare changes in cigarettes per smoking day from baseline to week 8.

5. Genetic Testing    N/A

A. Describe

- i. the types of future research to be conducted using the materials, specifying if immortalization of cell lines, whole exome or genome sequencing, genome wide association studies, or animal studies are planned *Write here*
- ii. the plan for the collection of material or the conditions under which material will be received *Write here*
- iii. the types of information about the donor/individual contributors that will be entered into a database *Write here*

HIC# 2000024740

iv. the methods to uphold confidentiality *Write here*

- B.** What are the conditions or procedures for sharing of materials and/or distributing for future research projects? *Write here*
- C.** Is widespread sharing of materials planned? *Write here*
- D.** When and under what conditions will materials be stripped of all identifiers? *Write here*
- E.** Can donor-subjects withdraw their materials at any time, and/or withdraw the identifiers that connect them to their materials? *Write here*
  - i. How will requests to withdraw materials be handled (e.g., material no longer identified: that is, anonymized) or material destroyed)? *Write here*
- F.** Describe the provisions for protection of participant privacy *Write here*
- G.** Describe the methods for the security of storage and sharing of materials *Write here*

6. **Subject Population:** Provide a detailed description of the types of human subjects who will be recruited into this study.

*Write here*

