**Sample Size Justification & Power Calculation:** This study is a developmental project testing the feasibility and potential efficacy of adding a novel intervention to enhance standard smoking cessation treatment. Sample size for the current study is based on guidelines for Stage 1 treatment development studies that suggest a minimum of 15 participants per experimental arm to obtain a reliable effect size estimate. Our target sample (25 per group) is sufficient to determine preliminary efficacy and estimate effect sizes for the binary cessation outcome, 7-day point prevalence abstinence at the end of treatment. This sample size produces two-sided 95% confidence intervals for the difference in population proportions with a half-width that is equal to 22%-24% when the difference in abstinence rates between groups (ST+ vs. ST) in estimated sample proportions is 10%-15% (e.g., 25% vs. 15%, 30% vs. 15%,

HIC# 2000024740

35% vs. 20%). For the continuous smoking outcomes, based on power=.80 and two-tailed alpha=.05, we can detect a statistically significant difference between groups of 4 days abstinent (SD=5) and a difference of 6 cigarettes per smoking day (SD=8) between baseline and end of treatment by group.

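### The planned baseline-to-week-8 ANOVA of cigarettes per smoking day leaves out the scheduled week-4 count, so a participant lost after week 4 contributes no week-4 information

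*Combined protocol and SAP*

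**What the plan says.** Section I, item 4 (Research Plan, Overview) sets the schedule: "Enrolled participants will complete research visits at 4 weeks and 8 weeks". Under Measures, the TLFB is listed for weeks 0, 4 and 8, to "obtain quantity and frequency estimates of tobacco use, alcohol, and other drugs for the 30-days prior to baseline and at each research visit". The Measures paragraph opens with a general statement: "Repeated measures will be used to assess changes in smoking and related constructs during treatment".

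The Analytical Plan (Aim 2) and Section I, item 12 (Statistical Considerations, Aim 2) name the same single analysis for cigarettes per smoking day: "a 2x2 mixed ANOVA (time x condition) to compare changes in cigarettes per smoking day from baseline to week 8". The two levels of time are baseline and week 8.

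The only missing-data rule is in the Analytical Plan: analyses follow intention to treat, "where missing data will be treated as smoking". No mixed model, imputation or sensitivity analysis is described for this outcome, and no dropout rate is given.

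**The concern.** The time-by-condition test of a 2x2 mixed ANOVA is a two-sample t-test on change scores, so a participant without a week-8 value has no change score. The missing-as-smoking rule works for a yes/no abstinence outcome but does not say how many cigarettes to enter. The participant is therefore either dropped or given a value by a rule the plan does not state, for example the baseline value. Neither route, as written, uses the count observed at week 4.

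Two things are at stake. One is precision, in a trial of 25 per arm with no allowance for dropout. The other is bias, if leaving after week 4 depends on week-4 smoking and does so differently by arm. Only ST+ receives alerts when smoking is detected, so reasons for leaving could differ, though the documents do not say that they will.

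**Working it through.** **The plan's own figure.** Item 12 states, "based on power=.80 and two-tailed alpha=.05", a detectable "a difference of 6 cigarettes per smoking day (SD=8) between baseline and end of treatment by group". With 25 per arm and 8 read as the SD of change, the standard error is 8 × √(2/25) = 2.263. The detectable difference is 2.263 × (1.960 + 0.842) = 6.34 (6.47 with the t distribution). Power for exactly 6 is 75.5% (73.8% with t). The stated 6 is met only by rounding down. That is a separate matter and does not affect this point.

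**Assumptions for the size of the effect (none is in the documents).** SD 8 at each visit. Correlations of 0.5 (baseline-week 4), 0.4 (baseline-week 8) and r = 0.6 to 0.8 (week 4-week 8). A share d = 20% to 30% is lost after week 4, and the two-point analysis uses completers only.

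**Precision under random loss.**
- Variance of change: 64 × 2 × (1 − 0.4) = 76.8. Completer SE of the contrast: √(76.8 × 2/20) = 2.77 at 20% loss and √(76.8 × 2/17.5) = 2.96 at 30%.
- If the observed visits explain a fraction R² of the variance of change, a likelihood model has variance proportional to (1 − R²)/(1 − d) + R². Relative to the completer analysis this is 1 − dR².
- Baseline alone: R² = 0.6²/1.2 = 0.30.
- Baseline and week 4: the R² for week 8 is (0.4² + r² − 2 × 0.4 × 0.5 × r)/(1 − 0.5²), which is 0.373 at r = 0.6 and 0.640 at r = 0.8. For change, R² = 1 − (1 − 0.373)/1.2 = 0.478 and 1 − (1 − 0.640)/1.2 = 0.700.

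SE ratios, the square root of 1 − dR²:

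| Loss | r | Weeks 0, 4, 8 vs completers | Weeks 0, 8 by likelihood vs completers | Added by week 4 (ratio of the two) |
|---|---|---|---|---|
| 20% | 0.6 | 0.951 | 0.970 | 0.981 |
| 20% | 0.8 | 0.927 | 0.970 | 0.957 |
| 30% | 0.6 | 0.926 | 0.954 | 0.970 |
| 30% | 0.8 | 0.889 | 0.954 | 0.932 |

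The total reduction is 5%-11% by this large-sample formula and about 4%-11% in simulation at 25 per arm. Week 4 itself accounts for about 2%-7%. The rest comes from keeping dropouts' baseline values.

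In power terms, take SD of change 8, a true difference of 6, 20% loss, and a correlation of 0.5-0.8 between week-4 and week-8 change. Completers give 66.0%, and using the week-4 change gives 68.2%-71.9%.

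**Bias when heavier week-4 smokers leave one arm only.** If the mean week-4 count among those retained in that arm falls by s standard deviations, the completer change is shifted by 8 × (r − 0.5) × s.
- Logistic dropout with slope 1 per SD of week-4 smoking gives s = 0.173 (20% loss) and 0.253 (30% loss). At 20% loss and r = 0.6 the bias is 8 × 0.1 × 0.173 = 0.14. At 30% loss and r = 0.8 it is 8 × 0.3 × 0.253 = 0.61.
- Varying the strength of this dependence gives about 0.1 to 1.1 cigarettes. The sign favours the arm losing its heavier smokers.
- The top of the range is 1.1/2.96 = 0.37, a little over a third of one SE.
- With week 4 in the model the bias is about 0, because dropout then depends only on observed data.

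**The case against.** The strongest reply is that this is largely preference. With complete data the week-8 contrast is essentially the same, the outcome is additional, and the trial is a pilot meant to estimate effect sizes. Remote visits and a $20 bonus for the last visit may keep loss after week 4 below 20%-30%; at 10% loss week 4 adds only about 1%-2%. All of this stands and limits the importance of the point. It does not give the week-4 count a role in the analysis.

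The proposed model is also incomplete without a definition for abstainers, whose cigarettes per smoking day is undefined. Left blank, successful quitters would be treated as missing at random. That stands too and is part of the fix.

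Several stronger readings are tempting but not supported:
- **That smoking is measured at week 4 in everyone.** The visit and the TLFB are scheduled for all; attendance is not guaranteed. The biochemical test is listed for the same weeks, but it is done when needed to confirm abstinence and is not a cigarette count.
- **That the whole precision gain comes from week 4.** Part of it comes from keeping dropouts' baselines.
- **That the plan prescribes completers only.** It does not say. The sizes above hold for that reading; filling in from baseline also ignores week 4 but was not quantified.
- **That the analysis contradicts the repeated-measures sentence under Measures.** That sentence introduces all the instruments, and a baseline/week-8 mixed ANOVA is itself a repeated-measures analysis.
- **That a bias of about 2 cigarettes should be expected.** Biases of 1.4-2.2 arise if exactly the worst 20% on week-4 change leave one arm, with SD of change 8. Nothing in the documents suggests so extreme a mechanism.

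**Conclusion.** The point holds for cigarettes per smoking day. The week-4 count is planned, and neither the named analysis nor the missing-data rule uses it. Under the stated assumptions the cost is a modest loss of precision, plus a small bias if dropout depends on week-4 smoking in one arm only. The dropout rate, the correlations and the dropout mechanism are all assumed.

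The protection has limits. It relies on missing at random, and participants lost before week 4 gain nothing from that visit. The point does not extend to 7-day abstinence at week 8, where missing-as-smoking is workable, or to total days abstinent, which could already draw on the week-4 interview. It is a free or cheap improvement, not a flaw that undermines the trial.

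**What to change.** In the Analytical Plan (Aim 2) and in item 12 (Aim 2), make these changes together:

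1. Define cigarettes per smoking day for a participant observed to be abstinent over the assessment window, so that this value is not treated as missing at random.
2. Replace the 2x2 ANOVA with a mixed model for repeated measures on the count at weeks 0, 4 and 8. Use time as a category, arm, time by arm, unstructured covariance, and Kenward-Roger or similar small-sample degrees of freedom. Report the week-8 time-by-arm contrast with its 95% confidence interval.
3. State that missing-as-smoking applies to the binary abstinence outcome, and that the cigarette model rests on missing at random.
4. Say how the existing allowance for transformation or non-parametric methods would apply to this model.

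The cost is some analysis wording and slightly more analysis work. No visit, measurement or sample-size change is needed. The trade-off is reliance on missing at random.

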**Inclusion Criteria:**

- (a) age 18 or older
- (b) daily cigarette smoker
- (c) seeking smoking cessation treatment at Yale TTS or Winchester chest clinic
- (d) able to read and write in English
- (d) owning a smartphone

**Exclusion Criteria:**

- (a) Unstable psychiatric/medical conditions (e.g., suicidal ideation, acute psychosis, dementia)
- (b) Current use of other tobacco products or regular use of combustible marijuana assessed via self-report

How will **eligibility** be determined, and by whom? *Write here*

Patients who are referred to tobacco treatment at TTS or Winchester chest clinic who are interested in participating will be contacted by our research staff and will be provided with additional information about the project. Interested participants will be initially screened by telephone to assess age, smoking status, and to ensure they are currently seeking smoking cessation treatment. Participants who meet initial eligibility screening will be scheduled for an intake session either remotely or in person. During the intake session, participants will complete an informed consent form. Following this, a research assistant will obtain medical and substance use histories, and may collect breath CO levels or cotinine measured by a small sample of urine or saliva. If study criteria are met, the participant will be randomized and scheduled for the subsequent sessions.

9. **Risks:** Describe the reasonably foreseeable risks, including risks to subject privacy, discomforts, or inconveniences associated with subjects participating in the research.

We feel that this research poses minimal risks to adults who are seeking treatment to stop smoking.

We provide a detailed description of risks below.

**Smoking Intervention Components:** The smoking intervention components pose minimal risk. All participants will receive standard outpatient tobacco treatment (ST) at the Yale Tobacco Treatment Service (TTS) or Winchester chest clinic following clinical practice guidelines. Patients receive up to 8 sessions of one-on-one counseling with a trained tobacco treatment specialist which focuses on setting a quit date within the first 2 weeks of treatment and discusses coping strategies and relapse prevention. Participants can obtain smoking cessation pharmacotherapy over the counter or by prescription from the smoking cessation provider. Participants will meet routinely with their provider to discuss their medication use. Additionally, wearing the smartband to track smoking behavior poses minimal risk. This technology passively monitors smoking behavior through wrist and arm movements using sensors in the smartband. When smoking is detected, an alert is sent to the users in the experimental condition through the band (vibration) and their smartphone app (alert) with a message indicating that smoking was just detected. The user can indicate yes/no if this smoking detection was accurate. Real-time smoking data is recorded for the user to review in their smartphone app and is available for the research team to view on a password-protected secure online dashboard. Data include only the timing and number of smoking events, labeled by subject ID.

**Interviews/Self-Report Questionnaires:** These are all noninvasive and should add no risk. The major disadvantages are the time taken to complete them, and possible breach of confidentiality. We have done our best to make the assessment schedule in this study as brief as possible. Also, our past experience with these measures indicates that they are acceptable to subjects. [name], a licensed clinical psychologist, will be available to meet with individuals and will provide staff with consultation should the need arise. Careful efforts aimed at maintaining confidentiality will be made, which are described below, and only participants' study numbers will be recorded on the forms themselves in order to protect confidentiality.

**Breath, saliva and urine collections:** Breath screening, saliva collections and urine collections should add no risks other than those normally associated with these procedures. Breath and

HIC# 2000024740

urine screens will be performed by appropriately trained research staff during the screening and research visits.

Loss of Confidentiality: Participants will be providing sensitive information, including their smoking and alcohol use behaviors. There are potential risks to subjects if such information were to be made public. Several procedures will help reduce the risk of disclosure of sensitive information, described in detail below.

Limits to Confidentiality: Participants will be informed that we will aim to protect their confidentiality and not reveal any personal information collected as part of the research procedures, including their reported smoking and other substance use history. All personnel to be involved in this study are already or will be certified by the Yale Human Investigation Committee (HIC) as having completed training in the protection of the rights of human subjects who participate in research. However, participants will be informed that if they report any information to us about child abuse or homicidal/suicidal behavior, we will be required to report this information to the appropriate authorities. These limits to confidentiality will be clearly stipulated in the consent form.

10. **Minimizing Risks:** Describe the manner in which the above-mentioned risks will be minimized.

*Write here*

